8.5.9 EXPLORATORY ANALYSES

The exploratory efficacy binary endpoints will be analyzed in the same manner as the primary hypothesis, but without the hypothesis test p-values. The efficacy time frame is defined in the same manner as for the primary endpoint. All of the efficacy binary endpoints will be analyzed in two ways: a) based on all lesions and b) based on qualifying and new lesions. Also, the Week 64/88 binary endpoints will be analyzed a) overall and b) according to three or four doses received.

Other analyses will examine the relationship between the primary efficacy endpoint and a) miRNA results, b) HRA results, c) cytology results, and d) HPV results. Relationships will be examined with contingency tables and/or logistic regression models which model the primary endpoint versus these results as regressor variables.

Post-baseline ELISA titers will be summarized with geometric means and associated t-distribution based 95% CIs. Post-baseline increases in ELISPOT will be summarized with medians and 95% CIs.

The change in tissue immune response magnitude will be summarized with means and associated t-distribution based 95% CIs.

Patient reported outcomes will be summarized with medians or proportions of subjects with endpoints and associated non-parametric or Clopper-Pearson 95% CIs, for continuous responses and binary responses, respectively.

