¹² An intra-anal and/or peri-anal lesion which is confirmed to be HPV-16 and/or HPV-18 positive and have histologically confirmed anal or anal/peri-anal HSIL evaluated by the Pathology Adjudication Committee (PAC).

¹³ Baseline photographic imaging is defined as photographs obtained pre-biopsy at Screening, or post biopsy at Screening (for subjects with historical biopsy tissue).

Exploratory Objectives	Associated Exploratory Endpoints
1. Describe the long term efficacy of VGX-3100 with respect to combined histopathologic regression of anal or anal/peri-anal HSIL and virologic clearance of HPV-16 and/or HPV-18	1. Proportion of subjects with no histologic evidence of anal or anal/peri-anal HSIL on histology (i.e. collected via biopsy or excisional treatment) and no evidence of HPV-16/18 at Week 64 by testing from intra-anal and/or peri-anal lesion tissue
2. Describe the long term efficacy of VGX-3100, as measured by histologic regression of anal or anal/peri-anal HSIL	2. Proportion of subjects with no evidence of anal or anal/peri-anal HSIL on histology (i.e. biopsies or excisional treatment) at Week 64
3. Describe the long term efficacy of VGX-3100, as measured by virologic clearance of HPV-16 and/or HPV-18 by testing from lesion tissue	3. Proportion of subjects with no HPV-16/18 at Week 64 by testing from intra-anal and/or peri-anal lesion tissue
4. Describe the long term efficacy of VGX-3100, as measured by virologic clearance of HPV-16 and/or HPV-18 by intra-anal swab testing	4. Proportion of subjects with no evidence of HPV-16 and/or HPV-18 from intra-anal swab by specific HPV testing at Week 64 and Week 88
5. Evaluate tissue immune responses to VGX-3100 in intra-anal and/or peri-anal samples	5. Assessment of proinflammatory and immunosuppressive elements in tissue, where feasible ¹⁴
6. Describe the clearance of HPV-16 and/or HPV-18 infection from non-anal anatomic locations	6. Proportion of subjects who have cleared HPV-16 and/or HPV-18 on specimens from non-anal anatomic locations as applicable based upon gender (i.e. oropharynx, cervical, vaginal, and penile at Week 36)
7. Describe the association of microRNA (miRNA) profile, previous anoscopy, cytology and HPV testing results with Week 36 histologic regression	7. HRA, cytology, and HPV test results and miRNA profile (baseline and at the Weeks 15 and 36) in conjunction with histologic regression of anal or anal/peri-anal HSIL at Week 36

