Pre-biopsy High Resolution Anoscopy Finding	Minimally required procedure
No lesion	Punch biopsy and photography; biopsy should be collected from within the approximate original boundaries of the study entry HSIL as proximal as possible to the original biopsy site which was previously determined to be HSIL by the PAC. New lesions or lesions that did not qualify at baseline should be biopsied at evaluation.
Single lesion (which was also present at baseline)	Punch biopsy and photography; biopsy should be collected within the boundaries of the original lesion and from the area most suspicious for advanced disease within the lesion by clinical exam. New lesions or lesions that did not qualify at baseline should be biopsied at evaluation.
Multiple lesions	Punch biopsies and photography; biopsy should be collected from the same lesions diagnosed as HSIL from study entry and from the area most suspicious for advanced disease within the lesion by clinical exam. New lesions or lesions that did not qualify at baseline should be biopsied at evaluation.

If HSIL is diagnosed in any Week 36 biopsy, but there is a reduction in the number of intra-anal and/or peri-anal lesion(s), reduction in peri-anal lesion(s) size or no change in peri-anal lesion(s) size from baseline (defined by Subgroup C), the Investigator has the option to administer a 4th dose of VGX-3100 at Week 40, and the subject will continue on the study to have HRA and biopsy at Week 64 of all lesions (qualifying and any other visible), i.e. the second efficacy checkpoint. Alternatively, the Investigator may instead choose to treat the subject with standard of care treatment (i.e. electrocautery, ablation, surgical excision), and the subject will continue on the study without further biopsy unless it is part of standard of care.

In the event of worsening anal or anal/peri-anal HSIL at any time during the trial (defined as any increase in lesion(s) area from baseline or worsening of anal or anal/peri-anal HSIL to cancer), the subject may receive standard of care treatment (i.e. electrocautery, ablation, surgical excision) per the Investigator's judgment but will continue on the study through Week 88 with HRA, but without further biopsy unless it is part of the standard of care.

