- ^c Screening 12-lead Electrocardiogram (ECG), complete blood count (CBC), serum electrolytes, blood urea nitrogen (BUN), creatinine (Cr), glucose, alanine aminotransferase (ALT), and Creatine Phosphokinase (CPK) performed within 45 days prior to first dose administration.
- ^d Negative spot urine pregnancy test is required for female subjects at Screening, prior to each study treatment, high-resolution anoscopy (HRA), and biopsy/surgical excision; the pregnancy test at Week 40 would only be needed for subjects who receive an additional dose.
- ^e At least 34 mL (4 x 8.5 mL yellow (ACD) tubes) whole blood and 4 mL serum per time point. At least 68 mL whole blood and 8 mL serum should be collected prior to first dose.
- ^f At least 51 mL (6 x 8.5 mL yellow (ACD) tubes) whole blood and 4 mL serum should be collected at Week 15.
- ^g Digital Anal Rectal Examinations (DARE) are to be performed once cytology has been collected and prior to HRA.
- ^h An additional visit may be scheduled to perform HRA if worsening of disease is suspected. Biopsies should not be performed at any visit other than at entry (Screening) and Weeks 36 and 64 for Subgroup C unless the Investigator suspects invasive cancer. All biopsy samples and/or excision samples must be sent to the Pathology Adjudication Committee (PAC) for review.
- ⁱ Photography of qualifying lesion(s) must be performed prior to and after biopsy, and at all HRA examinations. If a pre-biopsy digital photograph is not available for a historical biopsy sample at Screening, a post biopsy photo will be sufficient. Photographs of intra-anal lesion(s) will be for documentation purposes only. All qualifying peri-anal lesion(s) will be assessed using the ruler provided. The ruler should be placed in the field of vision and should be documented with photography at Screening, Day 0, and Weeks 4, 15, 28, 36, 64, and 88.
- ^j Tissue specimen (paraffin blocks) from all excised tissue lesion(s) that led to eligibility at study entry must be reviewed by the PAC and residual tissue from entry and Weeks 36 and 64 specimen(s) (paraffin blocks) must be sent to the central laboratory for immune analysis and Human Papillomavirus (HPV) testing.
- ^k Potential dosing at Week 40 is applicable for partial responders only.

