6.8 INJECTION AND ELECTROPORATION (EP)

Subjects will receive at least three doses of VGX-3100 (6 mg DNA/dose) in a volume of 1 mL by IM injection in the deltoid or lateral quadriceps muscles (preferably deltoid) followed immediately by EP with the CELLECTRA™ 5PSP. A fourth dose is optional for those assessed to be partial responders at the Week 36 efficacy assessment. Study treatment plus EP must not be given within 2 cm of a tattoo, keloid or hypertrophic scar, or if there is implanted metal within the same limb. EP may not be performed in the same arm adjacent to an implantable medical device (e.g., cardiac pacemaker, defibrillator or retained leads following device removal). The timing of the initial dose will be designated Day 0 with the subsequent doses scheduled for administration at Weeks 4, 12, and at Week 40 (for Subgroup C, [Figure 2](#) only). Please refer to the Investigator's Brochure for further information.

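### Section 8.5.9 models the composite endpoint where objective 7 names histologic regression, and its Week 64/88 split by doses sorts subjects by their Week 36 outcome

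*Protocol*

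**What the plan says.** All references are to protocol version 3.0.

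**Association analyses.** Exploratory objective 7 in the synopsis is to "Describe the association of microRNA (miRNA) profile, previous anoscopy, cytology and HPV testing results with Week 36 histologic regression". The paired endpoint 7 and Sections 3.5 and 3.6 name the same outcome. Section 8.5.9 instead provides for contingency tables and/or "logistic regression models which model the primary endpoint versus these results as regressor variables", where these results are miRNA, HRA, cytology and HPV. It gives no specimen or visit for the HPV results. Table 2 defines response on the composite as no HSIL, negative tissue PCR for HPV-16/18 and no curative treatment outside the study. A positive tissue PCR alone makes a subject a non-responder.

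**Week 64/88 analyses.** Section 8.5.9 states that "the Week 64/88 binary endpoints will be analyzed a) overall and b) according to three or four doses received". Exploratory binary endpoints are analysed like the primary one, "but without the hypothesis test p-values". On access to the fourth dose, footnote k of Table 8 says "Potential dosing at Week 40 is applicable for partial responders only", and Section 6.8 says "A fourth dose is optional for those assessed to be partial responders at the Week 36 efficacy assessment". The synopsis sets HSIL in a Week 36 biopsy as a condition (Subgroup C), after which "the Investigator has the option to administer a 4th dose of VGX-3100 at Week 40". Subjects without HSIL at Week 36 (Subgroups A and B) go on to Week 64 with no fourth dose. HSIL subjects may instead receive standard of care. Tables 2 to 7 score any curative treatment outside the study as non-response.

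**The concern.** There are two separate problems in one section.

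First, the dependent variable does not match the objective. A subject whose HSIL regresses but whose tissue stays HPV-positive counts as regressed under objective 7 and as a non-responder under Section 8.5.9. The analysis as written therefore answers a different question. It also puts HPV status on both sides of the model whenever the HPV result used is the Week 36 tissue PCR.

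Second, the number of doses received is decided after the Week 36 outcome is known, and largely by it. A table with three doses beside four doses invites the reader to take the difference as the effect of the fourth dose, and Section 8.2 still describes the exploratory efficacy analyses as concerning extended dosing. The three-dose row would mix the best Week 36 outcomes with failures assigned by rule, so it measures neither durability nor the absence of a fourth dose.

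**Working it through.** **The plan's own figure.** The protocol gives no figure for these exploratory analyses. Its one design figure, about 80% power for 40% against 15% at one-sided 0.05 (Section 8.6), reproduces by exact binomial calculation: with 21 evaluable, 7 responders are needed and power is 0.7998; with 24, 8 are needed and power is 0.808. This point does not touch it.

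**A. Association analyses**

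1. Outcome in objective and endpoint 7: Week 36 histologic regression. Outcome in Section 8.5.9: histologic regression and HPV-16/18 clearance. These differ with no arithmetic needed.
2. Tissue PCR is done at Screening and at Weeks 36 and 64. For a Week 36 outcome that leaves two tissue results. At Screening every subject is HPV-16/18 positive by inclusion criterion 4, although type 16 or 18 can vary. The Week 36 result is itself a component of the composite.
3. With Week 36 tissue PCR as regressor, P(response | positive) = 0 exactly, and P(response | negative) = 0.40/c, where 0.40 is the protocol's assumed response rate and c is the share clearing tissue (assumed):
   - c = 0.45: 0.889
   - c = 0.50: 0.800
   - c = 0.60: 0.667
   - c = 0.70: 0.571

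   One cell is a structural zero, so a logistic model has quasi-complete separation and an infinite odds ratio. The other cell is free.
4. With the Week 36 swab, assume c = 0.50 and agreement a with tissue in both directions, unrelated to histology. The swab-negative share is then 0.50, and P(response | swab-negative) = 0.40a/0.50, while P(response | swab-positive) = 0.40(1 - a)/0.50:
   - a = 0.60: 0.48 and 0.32
   - a = 0.75: 0.60 and 0.20
   - a = 0.90: 0.72 and 0.08

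   Neither cell is determined by definition.

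**B. Split by doses**

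Let h be the share without HSIL at Week 36, q the share of the remainder given dose 4, k the share of Week 36 regressors still responding at Week 64, and l the late response rate among dose-4 subjects when dose 4 has no effect at all. HSIL subjects not given dose 4 are taken to have standard of care with curative intent and so score zero. Then:

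- three-dose row = hk / [h + (1 - h)(1 - q)]
- four-dose row = l

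All four inputs are assumptions: h = 0.4, 0.5, 0.6; q = 0.3, 0.6, 0.9, 1.0; k = 0.5, 0.7, 0.9; l = 0.1, 0.2, 0.4. That is 3 × 4 × 3 × 3 = 108 scenarios.

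- Middle case, h = 0.5, q = 0.6, k = 0.7, l = 0.2: 0.35/0.70 = 50% against 20%, a 30-point gap from selection alone.
- Largest gap, h = 0.6, q = 1.0, k = 0.9, l = 0.1: 0.54/0.60 = 90% against 10%, +80 points.
- Smallest, h = 0.4, q = 0.3, k = 0.5, l = 0.4: 0.20/0.82 = 24.4% against 40%, -15.6 points.
- The three-dose row is ahead in 101 of 108 scenarios; in the other 7 it is not.

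The same in counts of 24, again assumed: 10 regress at Week 36 and 9 stay clear. If 7 of the 14 with HSIL get dose 4 (1 responds) and 7 get standard of care, the rows are 9/17 = 53% and 1/7 = 14%. If 2 get dose 4 (1 responds) and 12 get standard of care, they are 9/22 = 41% and 1/2 = 50%. The sign depends on how many HSIL subjects are sent to standard of care, which the investigator decides.

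**The case against.** The best defence is that nothing here is inferential. Exploratory endpoints carry no p-values, Section 8.3 allows only one formal hypothesis, the version 3.0 exploratory objectives speak of long-term efficacy, and no contrast of three with four doses is set out. Selection for dose 4 is disclosed, and the four-dose row already is the group with HSIL at Week 36 who received it. On the HPV model, no specimen or visit is named, objective 7 speaks of previous results, and the Week 15 and 36 time points in endpoint 7 directly follow the miRNA profile. Swabs are taken at eight time points and cover other high-risk types, so non-circular predictors exist. Contingency tables are allowed in place of logistic regression.

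Much of this stands, and it limits how far the point goes. A reader might infer that both exploratory answers are fixed in advance. The documents do not support that: Week 64 response rests on new biopsies, regressors can recur, dose-4 subjects can respond, and only the cell positive by Week 36 tissue PCR is a structural zero. A reader might also infer that the table must make the fourth dose look harmful. It usually would under the assumed rates, but the rule scoring outside treatment as failure pulls the three-dose row down and the sign can reverse.

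The defence does not remove two things. The outcome in Section 8.5.9 is not the one in objective 7, under any choice of HPV specimen. And leaving out p-values does not remove confounding from the estimates and their intervals.

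**Conclusion.** The point holds in two limited parts.

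The mismatch of outcomes follows from the text alone and needs no assumptions. The circularity follows from Table 2 but applies only if Week 36 tissue PCR is used as a predictor of the composite.

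The dose split is confounded by Week 36 outcome. The direction is usually, not always, in favour of three doses. The range of -16 to +80 points and the 101 of 108 scenarios rest on assumed rates for Week 36 regression, allocation to dose 4, durability and late response, and on every HSIL subject without dose 4 being scored a failure. No particular gap should be quoted as the expected one.

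Both parts concern exploratory analyses. The primary test and its conclusion are unaffected. The correction is worth making because it is nearly free and because Section 8.1 presents these sections as the formal analysis plan.

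**What to change.** 1. In Section 8.5.9, make Week 36 histologic regression the dependent variable of the association analyses, as objective and endpoint 7 state. Table 3 already defines responders for it. Name the specimen and visit of the HPV results. If the composite is also modelled, do not use Week 36 tissue PCR as a predictor.
2. Replace the split by number of doses with Week 64/88 results by Week 36 status: no HSIL at Week 36 (read as durability); HSIL with dose 4; HSIL without dose 4, showing how many of the last group are failures by the rule on outside treatment.
3. State that no difference between rows is an effect of the fourth dose. Make no comparison of dose 4 with no dose 4 within the HSIL group either: subjects given standard of care with curative intent fail by rule and have no further study biopsy unless it is part of that care, so such a comparison would favour dose 4 through the scoring.

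The cost is wording and table shells, with no new data, subjects or procedures. The downside is small cells, which support description only.

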8. Describe patient reported outcomes (PRO) for subjects treated with VGX-3100	8. Patient reported outcome (PRO) endpoints prior to first dose (Day 0), on the day of and following each dose, and at Weeks 36, 64, and 88. There will be an

	additional PRO assessment at Week 40 if a subject receives a 4 th dose
9. Determine the humoral and cellular immune response following dose 3 and additional time points compared to baseline	9a. Levels of serum anti-HPV-16 and anti-HPV-18 antibody concentrations at baseline and Weeks 15, 36, and 88 9b. Interferon- γ ELISpot response spot forming units (SFU) at baseline and Weeks 15, 36, and 88
10. Determine the long term efficacy of VGX-3100 with respect to histopathologic regression of anal or anal/peri-anal HSIL or virologic clearance of HPV-16 and/or HPV-18	10. Proportion of subjects with no histologic evidence of anal or anal/peri-anal HSIL on histology (i.e., collected via biopsy or excisional treatment) or no evidence of HPV-16 and/or HPV-18 at Week 64 from intra-anal and/or peri-anal lesion

¹⁴ Additional assessments may include visualization of PD-L1, Granulysin, Perforin, CD137, CD103 and possible other relevant markers identified in the literature as sample allows.

[figure not shown]
Study Design:

HPV-203 is a Phase 2, open-label efficacy study of VGX-3100 (DNA plasmids encoding E6 and E7 proteins of HPV types 16 and 18) administered by IM injection followed by EP in adult men and women who are HIV negative with histologically confirmed anal or anal/peri-anal HSIL associated with HPV-16 and/or HPV-18.

Approximately 24 subjects will receive at least 3 doses of VGX-3100. Each dose of VGX-3100 will be administered in a 1 mL volume IM followed immediately by EP. As shown in **Figure 1**, study subjects will receive at least 3 doses of VGX-3100 depending upon their disposition with regard to histologic and lesion area changes during the trial. The first dose will be administered on Day 0, the second at Week 4, and the third at Week 12. Partial response to VGX-3100 may still be of medical importance by being able to limit the extent of surgery necessary. For partial responders at Week 36, a fourth dose may be administered at Week 40.

All subjects are scheduled to be followed to Week 88.

Figure 1: HPV-203 Study Visit Schedule

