3.5 EXPLORATORY OBJECTIVE(S)

- Describe the long term **efficacy** of VGX-3100 with respect to combined **histopathologic regression** of anal or anal/peri-anal HSIL and **virologic clearance** of HPV-16 and/or HPV-18
- Describe the long term **efficacy** of VGX-3100, as measured by **histologic regression** of anal or anal/peri-anal HSIL
- Describe the long term **efficacy** of VGX-3100, as measured by **virologic clearance** of HPV-16 and/or HPV-18 by testing from lesion tissue
- Describe the long term **efficacy** of VGX-3100, as measured by **virologic clearance** of HPV-16 and/or HPV-18 by intra-anal swab testing

- Evaluate tissue immune responses to VGX-3100 in intra-anal and/or peri-anal samples
- Describe the **clearance** of HPV-16 and/or HPV-18 infection from non-anal anatomic locations
- Describe the association of microRNA (miRNA) profile, previous anoscopy, cytology and HPV testing results with Week 36 histologic regression
- Describe the patient reported outcomes (PRO) for subjects treated with VGX-3100
- Determine the humoral and cellular immune response following administration of VGX-3100 at post dose 3, and after additional dosing compared to baseline
- Determine the long term **efficacy** of VGX-3100 with respect to histopathologic regression of anal or anal/peri-anal HSIL or virologic clearance of HPV-16 and/or HPV-18

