6.14 PERIPHERAL BLOOD IMMUNOGENICITY ASSESSMENTS

Whole blood and serum samples will be obtained at baseline (Screening and Day 0 prior to dosing) and at Weeks 15, 36, and 88. Details of the immunology sample collection and shipment information will be provided in the Laboratory Manual.

A standardized binding enzyme-linked immunosorbent assay (ELISA) may be performed to measure the anti-HPV-16/18 Ab response induced by VGX-3100.

Peripheral Blood Mononuclear Cells will be isolated from whole blood samples. Assessment of cellular immune activity may occur via the application of the Interferon- γ enzyme-linked immunosorbent spot (IFN- γ ELISpot) assay as well as flow cytometry.

Additional assessment of cellular immune activity will occur via the application Flow Cytometry for the purposes of performing a Lytic Granule Loading Assay. The Lytic Granule Loading assay may examine the following external cellular markers: CD3, CD4,

CD8 (T cell identification), CD137, CD38 and CD69 (T cell activation markers) as well as PD-1 (exhaustion/activation marker). The Lytic Granule Loading assay may additionally analyze the following intracellular markers: Granzyme A, Granzyme B, Granulysin and Perforin (proteins involved in lytic degranulation and cytotoxic potential). Markers examined in this assay may change as new relevant data become available.

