8.5.2 SECONDARY ANALYSES

The secondary efficacy binary endpoints will be analyzed in the same manner as the primary hypothesis, but without the hypothesis test p-values. The efficacy time frame is defined in the same manner as for the primary endpoint. All of the efficacy binary endpoints will be analyzed in two ways: a) based on all lesions and b) based on qualifying and new lesions.

The anatomic extent endpoint will be analyzed by calculating the mean percent change in surface area and the mean percent change in number of lesions and associated 95% t-distribution based confidence intervals.

Post-baseline increases in Flow responses will be summarized with medians and 95% CIs. Valid samples for statistical analysis purposes will be those collected within 14 days of the specified visits. Baseline is defined as the last measurement prior to the first treatment administration.

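### The antibody analysis in 8.5.9 fixes only post-baseline geometric mean titres, although the objective is the response compared to baseline in a single-arm trial of subjects infected at entry

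*Protocol*

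**What the plan says.** All references are to protocol version 3.0.

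- **Objective.** Synopsis, exploratory objective 9: "Determine the humoral and cellular immune response following dose 3 and additional time points compared to baseline". Section 3.5 repeats it: "Determine the humoral and cellular immune response following administration of VGX-3100 at post dose 3, and after additional dosing compared to baseline".
- **Endpoint.** Synopsis, endpoint 9a: "Levels of serum anti-HPV-16 and anti-HPV-18 antibody concentrations at baseline and Weeks 15, 36, and 88".
- **Assay.** Section 6.14 says that a binding ELISA "may be performed to measure the anti-HPV-16/18 Ab response induced by VGX-3100". Serum is drawn at Screening and Day 0 before dosing, then at Weeks 15, 36 and 88.
- **Antibody analysis.** Section 8.5.9: "Post-baseline ELISA titers will be summarized with geometric means and associated t-distribution based 95% CIs".
- **Other immune measures.** The next sentence of 8.5.9 reads "Post-baseline increases in ELISPOT will be summarized with medians and 95% CIs". Section 8.5.2 reads "Post-baseline increases in Flow responses will be summarized with medians and 95% CIs". Section 8.5.9 also summarises tissue immune response as a change.
- **Setting.** Section 8.2 describes a single-arm trial. Inclusion criterion 4 requires PCR-confirmed HPV-16/18 infection. The exclusion of prior therapeutic HPV vaccination expressly permits licensed prophylactic vaccines.
- **Status of section 8.** Section 8.1 says that the sections after it are the formal statistical analysis plan.

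**The concern.** The objective is a comparison with baseline, but the statistic fixed for it is a level at a later visit. Without a control arm, each subject's own pre-dose value is the only reference for an induced response. Infection at entry and permitted prophylactic vaccination mean that antibody before dose 1 cannot be assumed absent. Analysts who follow 8.5.9 literally would produce a table with no comparison to baseline, and the humoral half of objective 9 would go unanswered even though the serum needed to answer it has been drawn.

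**Working it through.** The protocol gives no antibody figure, so there is nothing to reproduce. The check compares the passages and then illustrates the consequence.

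**1. The four immune measures side by side**

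| Measure | Section | Quantity summarised |
|---|---|---|
| Flow cytometry | 8.5.2 | post-baseline increase, median |
| ELISpot | 8.5.9 | post-baseline increase, median |
| Tissue response | 8.5.9 | change, mean |
| ELISA | 8.5.9 | post-baseline titre, geometric mean |

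Only the ELISA is specified as an absolute level. ELISA and ELISpot stand in adjacent sentences, and the second says increases while the first does not.

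**2. What the post-baseline GMT contains**

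In subjects with both samples, the mean post-baseline log titre equals the mean baseline log titre plus the mean log change. Hence

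GMT(post) = GMT(baseline) × geometric mean fold rise.

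One number on the left cannot identify two on the right.

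**3. Illustration (assumed titres, SD and correlation; none is in the documents)**

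Take n = 22, which is the 24 subjects and 90% evaluable of section 8.6: 24 × 0.9 = 21.6. Assume an SD of log10 titre of 0.6 at both times and a within-subject correlation r of 0.5 or 0.8.

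- Half-width for the GMT: t × SD/√n = 2.080 × 0.6/√22 = 0.266 on the log10 scale, a factor of 10^0.266 = 1.845.
- Baseline GMT 200, no induced response: post-baseline GMT 200, 95% CI 200/1.845 to 200 × 1.845 = 108 to 369.
- Baseline GMT 50, true 4-fold rise: post-baseline GMT 50 × 4 = 200, 95% CI 108 to 369.

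The planned output is identical in the two cases. For the paired fold rise, the SD of the log change is 0.6 × √(2(1−r)):

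| True situation | Fold rise (95% CI), r = 0.5 | Fold rise (95% CI), r = 0.8 |
|---|---|---|
| Baseline 200, no response | 1.0 (0.54 to 1.85) | 1.0 (0.68 to 1.47) |
| Baseline 50, 4-fold rise | 4.0 (2.17 to 7.38) | 4.0 (2.72 to 5.89) |

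The fold rise separates them.

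**4. Precision**

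With equal SDs, the variance of the paired log change relative to that of the single post-baseline log titre is 2(1−r):

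| r | Variance ratio | Interval width ratio (square root) |
|---|---|---|
| 0 | 2.0 | 1.41 |
| 0.3 | 1.4 | 1.18 |
| 0.5 | 1.0 | 1.00 |
| 0.7 | 0.6 | 0.77 |
| 0.8 | 0.4 | 0.63 |

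The paired interval is narrower only if r exceeds 0.5. Precision is therefore not an argument for the change.

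**The case against.** The strongest reply is that endpoint 9a is defined as antibody levels at baseline and later visits, and a geometric mean is a direct summary of a level. Section 8.5.9 does not forbid a baseline row. If one were shown, the ratio of the two GMTs in subjects with both samples would equal the geometric mean fold rise. On this view only a table column is missing, which is a matter for table shells. The endpoint is also exploratory, the assay is optional, and positive lesion PCR does not show that this ELISA, whose antigen is not named, would detect antibody at baseline.

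Much of this stands. It limits the importance of the point and leaves the practical size of the problem unknown. It does not remove the mismatch. The analysis text specifies post-baseline titres and nothing else, the neighbouring measures show that the authors had wording for an increase, and two separate GMTs give no interval for the within-subject change. Section 8.1 makes section 8 the formal plan, so the point is about a method that was fixed, not about detail left for later.

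A reader might infer that the protocol treats the post-baseline GMT as the vaccine response, or that the GMT is biased. The documents support neither. No rule of interpretation is given, section 6.14 describes the purpose of the assay and not how to read its result, and the GMT is a proper estimate of the level at its own visit.

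**Conclusion.** The point holds as a minor one. The antibody summary fixed in 8.5.9 does not answer an objective framed as a comparison with baseline. In a single-arm trial of subjects infected at entry, it cannot by itself separate induced from pre-existing antibody. That conclusion follows from the identity in the working and needs no assumed titres.

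How much it matters in practice depends on baseline titres, which the documents do not give. If they are low or undetectable, little is lost; if they are substantial, a post-baseline GMT says little about induction. The figures of 200 and 4-fold illustrate the ambiguity and do not estimate it.

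A gain in precision should not be inferred either, since it depends on an unknown correlation and reverses below 0.5. The single formal hypothesis, the efficacy conclusion and the error rate are untouched.

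**What to change.** In 8.5.9, replace the ELISA sentence with wording such as: *For anti-HPV-16 and anti-HPV-18 separately, the within-subject geometric mean fold rise from baseline (last value before first dose) will be reported with t-based 95% CIs on the log scale at Weeks 15, 36 and 88. Geometric mean titres at baseline and each of these visits will be shown alongside. Titres below the detection limit will be set to [stated value].*

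These visits match endpoint 9a, the Schedule of Events and section 6.14. Section 3.6 still lists Week 64 for antibody, although no serum is scheduled then, and should be aligned. The baseline definition can be carried over from 8.5.2.

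The cost is small: no new sample, visit or test, and the planned GMTs are kept. There are two consequences. The substitution value must be chosen in advance, because it determines the fold rise wherever the baseline is undetectable. Subjects without both samples do not contribute to the fold rise, since section 8.5.8 imputes nothing beyond adverse event dates; the number of pairs should be shown at each visit.
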